Certified letter. The linkage coordinator will offer to mail a certified letter about the study to eligible potential participants who are successfully contacted but do not verify their identity. The letter is intended to legitimize the study and personalize contact with the potential participant. The certified letter will be similar to the mailed introductory letter, although it will have the option to include some tailored language referencing a prior conversation between the eligible potential participant and the linkage coordinator. The letter will include safeguards—including a general description about the nature of the study and general study team contact information—to protect confidentiality and minimize the risk of HIV status disclosure. Eligible potential participants who are sent a certified letter will be re-contacted by the linkage coordinator according to procedures described above.

Procedures: Usual care arm

The Usual Care arm will involve an artificial control sample created through propensity score matching. No contact will occur with these individuals and they will receive no study-specific intervention, consistent with state-level care for late ART prescription refill(s) for Virginia Medicaid enrollees living with HIV in Virginia. Detail for other processes and procedures for this arm are below.

Screening. Screening for controls will occur over the month enrollment period and as described above.

Recruitment. Recruitment of eligible potential participants in the control (Usual Care arm) does not apply. No contact will occur with these individuals.

Informed consent. Informed consent procedures do not apply. Only existing, secondary health information will be used. This health information will be de-identified, with no code key available; consent and HIPAA authorization do not apply.

Follow-up. A 3-month follow-up period will begin on the first date an eligible control is confirmed as having a late ART prescription refill(s) by >30–365 days.

Procedures: Program arm

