Phase 1. Phase 1 is for participants with late ART prescription refill(s) by >30–60 days. The phone consultation will involve a 30-minute discussion of the participant’s barriers to filling their ART prescription and referrals to resources that may address these barriers. The consultation will use a conversational format guided by scripted prompts. During the consultation, the linkage coordinator will document data on each participant’s self-reported barriers to filling ART prescriptions. Referrals will be made to existing resources that are already offered through the participant’s Medicaid managed care organization or through pharmacists, their HIV provider, or local community resources. If a participant self-reports multiple barriers to filling ART prescriptions, the participant will be asked to prioritize the barriers; this will allow the linkage coordinator to provide referral information that aligns most closely with participant preferences. Whenever possible, the primary referral will involve a warm hand-off, where the linkage coordinator introduces the participant directly to the referral resource in real-time. This approach is designed to engage the participant and maximize success in the referral process. If a warm hand-off is not possible at the time of the consultation, a follow-up call can be scheduled to make the warm hand-off; referral contact information will be offered to the participant after 3 unsuccessful warm hand-off attempts. Participants will additionally be given contact information for referrals involving 1-2 other prioritized barriers. The referral resource, referral date, and referral time will be documented by the linkage coordinator. Approximately ten business days after the Phase 1 referral, the participant’s ART prescription claims will be followed in the Medicaid claims data. The 10-business-day threshold will allow adequate time for an ART prescription fill and prescription claim reimbursement. If the participant has an ART prescription claim after this 10-business-day period, the participant will not be contacted further. If the participant has no ART prescription claim after the 10-business-day period, the participant will be eligible for Phase 2.

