Phase 2. Phase 2 is for participants with late ART prescription refill(s) by >60 days. Phase 2 will involve a more intensive phone consultation, in which more complex barriers may be assessed. Three phone contact attempts will be made in the same manner as in Phase 1. Participants who do not respond to these contact attempts, who do not verify their identities, or who do not either consent to participate or assent to continue to participate will not be contacted further. The linkage coordinator will guide a 30-minute consultation similar in format to Phase 1. In Phase 2, however, more complex barriers, such as substance use and mental health concerns, will be probed and referrals made accordingly. Participants in Phase 2 will also be offered PositiveLinks, an evidence-based mobile app designed to support ART adherence and retention in care (<https://www.positivelinks4ric.com/>). PositiveLinks is based on theories of behavior change and provides 1) daily check-ins on mood, stress, and medication adherence, which promote self-monitoring; 2) educational resources for users; 3) direct messaging with study linkage coordinators; 4) an anonymous message board to connect with peers living with HIV to provide and receive social support; and 5) contact information for patients’ providers and pharmacies. A major strength of the app is its support of self-monitoring, which addresses intrapersonal barriers to ART adherence. The app contains data security measures designed to protect patient privacy and confidentiality (e.g., phone calls to providers made through the app do not appear in the phone’s call log). Further details on the app’s development, user functions, and security features are available in the uploaded supporting documents. We emphasize that all study participants will be enrolled in Virginia Medicaid, and contracted Medicaid managed care organizations provide smartphones for enrollees (see

<https://www.virginiamanagedcare.com/choose/compare-plans>); therefore, we do not anticipate that smartphone ownership will be a barrier to participants' enrolling in PositiveLinks.

Follow-up. A 3-month follow-up period will begin on the date of the final consultation (**Table 1**).

Table 1. Start date of 3-month follow-up for participants receiving patient-level support

Phase(s) received	Start of 3-month follow-up
Phase 1 only	Date of final phase 1 consultation
Phase 2 only	Date of final phase 2 consultation

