Phases 1 and 2	Date of final phase 2 consultation or joining of PositiveLinks*

* Most recent date will be selected; does not include direct messaging support provided via PositiveLinks.

Outcomes

Outcomes will be at the participant level. The primary outcome will be HIV viral suppression, defined as the most recent HIV RNA viral load <200 copies/mL at 3-month follow-up. In the usual care arm, 3-month follow-up will be the first date an eligible control is confirmed as having a late ART prescription refill(s) by >30–365 days; in the program arm, 3-month follow-up will be as shown in Table 1. The secondary outcomes will be adherence (defined as the proportion with ART prescription claims covering >90% of enrolled coverage days) and the number and percentage of participants reinitiating late ART prescription.

Statistical analysis

Descriptive statistics. We will evaluate the balance of demographics and other patient characteristics, as well as the measures between the 2 treatment groups (those enrolled in the Program arm, and those in the Usual Care [control] group). We will compare the means and medians of the continuous variables and test the differences between the treatment samples using t-tests and Kruskal-Wallis tests. Systemic differences between the enrolled participants enrolled and the control might introduce selection bias.

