inclusion and Virginia Medicaid–Virginia Department of Health matching protocols, we note that no missing data are allowed.

Other data and analyses

Other data to be collected through interactions with participants include the quality improvement initiative's process data. These data will be used to track study progress and facilitate recruitment and enrollment (e.g., number and timing of contact attempts, mailing address for optional certified letter), current ART use to determine final eligibility (i.e., confirmation that the participant has not refilled their ART prescription), and barriers discussed and referrals made.

Additionally, PositiveLinks app metadata and usage data will be collected through the PositiveLinks app. App metadata include: number of app launches, number of app log ins, response rates for daily queries about medication, response rates for daily queries about mood, response rates for daily queries about stress, response rates for weekly quizzes, number of posts to community message board, number of direct messages to linkage coordinator, and number of times visiting resources section. The text of community board posts will also be collected.

Descriptive statistics will be used to summarize recruitment and enrollment, barriers endorsed, referrals made, and PositiveLinks app usage. We may examine correlates of these variables and/or consider these variables as confounders in the primary evaluation analyses. Community board posts from the PositiveLinks app will be examined using textual analysis methods.

Data management

Data management and statistical analysis will be performed using Terradata 16.10, REDCap 10.9.4, and SAS® Software version 9.4 (or most recent VCU- and agency-approved software releases available). Statistical analysis will occur at Virginia Medicaid, Virginia Department of Health, VCU, University of Virginia, and CDC. Intermediate datasets will be stored on Virginia Medicaid servers, Virginia Department of Health servers, and University of Virginia servers. Final limited and de-identified datasets will be stored at Virginia Medicaid, as well as Virginia Department of Health, and also securely transferred to VCU and CDC.

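### The 3-month clock starts at first confirmed lateness for controls but at the final consultation for Program participants, so the arms can differ with no program effect, in a direction not known in advance

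*Combined protocol and SAP*

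**What the plan says.** **Usual care arm.** The Follow-up paragraph under Procedures: Usual care arm reads: "A 3-month follow-up period will begin on the first date an eligible control is confirmed as having a late ART prescription refill(s". The lateness range it applies is >30–365 days. The Outcomes section repeats this in a looser form: "In the usual care arm, 3-month follow-up will be the first date an eligible control is confirmed as having a late ART prescription refill(s". Read literally, that makes the start date the follow-up itself.

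**Program arm.** Under Procedures: Program arm, Follow-up: "A 3-month follow-up period will begin on the date of the final consultation". For participants who receive both phases, Table 1 gives "Date of final phase 2 consultation or joining of PositiveLinks", whichever is later.

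**What comes before the Program clock.** Recruitment takes about two weeks per monthly screen and can extend over more than one month (up to three calls a month, six in all). Identity verification and consent follow. Other data and analyses adds, as part of final eligibility, "confirmation that the participant has not refilled their ART prescription". No comparable later check is described for controls, who are never contacted.

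**Who gets the later clock.** From the Phase 1 paragraph: "If the participant has no ART prescription claim after the 10-business-day period, the participant will be eligible for Phase 2". From the Phase 2 paragraph: "Phase 2 is for participants with late ART prescription refill(s) by >60 days".

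**Primary outcome.** Viral suppression is "defined as the most recent HIV RNA viral load <200 copies/mL at 3-month follow-up". No earliest date for an eligible result is given.

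**The concern.** The two arms are followed from different events, and three consequences follow.

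1. **Selection at entry.** A Program participant must still be unfilled at the time of contact. A control who refills the day after confirmation stays in and counts as a success. This favors controls if refill rates fall with time, is neutral if they are constant, and favors the Program arm if they rise.
2. **A restart triggered by an early outcome.** A Phase 1 participant who refills keeps that success. One who does not, and who receives Phase 2, gets a fresh 3-month window. Controls get no second window. For reinitiation this can only favor the Program arm.
3. **Test timing.** The most recent viral load may predate the window, so moving the window changes which result is used.

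The covariates named under Statistical analysis are patient, provider, hospital and geographic characteristics. Balancing them does not align start dates or undo a restart that happens after entry. The observed difference would mix program effect with clock effect, and neither a positive nor a null result could be attributed cleanly to the program.

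**Working it through.** The plan gives no figure for this effect, so there is none to reproduce. The check asks what gap the two clocks create when the program has no effect.

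**From the documents:** both start rules, the roughly two-week recruitment period, the 10-business-day check (taken as 14 days), the >60-day Phase 2 rule, about 100 per arm, and a 50% control suppression rate (used for the rejection rates below).

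**Assumed:** 50% of controls refill by day 90; first consultation 7–21 days after confirmation; half the arm enters in Phase 1, 30–60 days late at confirmation; Phase 2 held 0–1, 7–21 or 14–45 days after the 10-business-day check and not before day 60 of lateness. Refill rates are falling (gamma frailty variance 1 or 0.5), constant (exponential) or rising (Weibull shape 1.25 or 1.5).

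**Formulas.** Let S(t) be the probability of being unfilled t days after confirmation, L the first-consultation day and G the days from there to Phase 2.

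- Control: 1 − S(90) = 50%.
- Program, no restart: 1 − S(L+90)/S(L).
- Program, restart if still unfilled: 1 − S(L+G+90)/S(L).

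**Selection alone.** With frailty variance 1, S(t) = 90/(90+t). At L = 14: S(104) = 0.464, S(14) = 0.865, so 1 − 0.464/0.865 = 46.4%, a gap of -3.6 points.

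**Restart alone.** At a constant rate h = ln 2/90 = 0.0077 per day, selection has no effect. With G = 14 + 14 = 28: 1 − 0.5 × exp(−0.0077 × 28) = 1 − 0.5 × 0.806 = 59.7%, a gap of +9.7 among Phase 1 entrants and about +4.8 over the whole arm.

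**Reinitiation gap, Program minus control, in points.** The three values are for the three Phase 2 delays.

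| Refill rate | No restart | Phase 1 entrants, all unfilled get Phase 2 | Whole arm, all unfilled get Phase 2 | Whole arm, half get it |
|---|---|---|---|---|
| Falling, variance 1 | -3.6 | 0.5, 3.4, 6.4 | -1.5, -0.1, 1.5 | -2.5, -1.7, -1.0 |
| Falling, variance 0.5 | -1.8 | 2.8, 6.3, 9.9 | 0.5, 2.3, 4.0 | -0.6, 0.3, 1.2 |
| Constant | 0 | 5.4, 9.7, 14.2 | 2.7, 4.8, 7.1 | 1.4, 2.4, 3.5 |
| Rising, shape 1.25 | +3.3 | 9.7, 14.8, 20.1 | 6.5, 9.1, 11.7 | 4.9, 6.1, 7.5 |
| Rising, shape 1.5 | +5.8 | 13.2, 19.1, 25.2 | 9.5, 12.5, 15.5 | 7.6, 9.1, 10.5 |

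**Effect on the test.** Exact rejection rates of the chi-squared test with 100 per arm and a 50% control rate: gap 0, 5.6%; +2.2, 6.8%; +7.1, 18.3%; +15.5, 61.5%.

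**Viral suppression, by simulation.** Suppression is assumed 14–56 days after refill, and all still unfilled receive Phase 2.

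- Tested on the last day of the window: -1.2 to +8.7 (constant or falling rates), +7.0 to +18.4 (rising).
- Latest result on average 60–180 days old, pre-confirmation results counted and 30–80% of those suppressed: -7.0 to +3.1 and -5.8 to +8.7.
- Mid case (constant rate, Phase 2 delay 7–21 days, suppression at 28 days, mean age 120 days, 50% suppressed earlier): -1.8. The same case tested on the last day: about +6.

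**Sensitivity.** If 20% rather than half enter in Phase 1, the whole-arm reinitiation gap is -2.7 to +2.8 for constant or falling rates. With a first-consultation lag of 30–60 days and no restart it is -9.8 to +14.0. A separate closed-form model (lag 0.5–2 months, Phase 1 to Phase 2 gap 0–1 month, frailty variance 0–2) puts the Program rate at 29% to 60% against 50% in controls.

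**With aligned clocks.** A shared first-consultation time zero and a fixed 90- or 150-day horizon leave every scenario within 0.15 points of zero for both outcomes.

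**The case against.** The strongest reply is that Table 1 is deliberate: it measures outcomes 3 months after support is delivered, and uncontacted controls have no consultation date. That explains the Program clock. It does not make the between-arm comparison valid, because the control clock was not moved to match.

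Several criticisms of the sizes stand:

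- The 50% Phase 1 share has no source in the documents, and a 20% share shrinks the gap.
- The 7–21 day lag is narrow given that calls may run into a second month. A longer lag widens the range in both directions.
- The largest figures need refill rates that rise with time late. The plan links longer lateness to more complex barriers, which if anything suggests falling rates.
- The primary outcome's mid case is small: a 1.8-point gap is declared significant 6.4% of the time, against 5.6% with no gap.
- Adherence was not modelled, and the secondary outcomes do not restate the 3-month window. The general follow-up rules for each arm reasonably cover them.
- The near-zero residual after alignment holds by construction, in a model with exchangeable arms and fully observed refills. A claims check in real data is subject to claim delay and is not the same as asking the participant.

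These points affect how large the bias might be. None removes the misalignment.

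**Conclusion.** The concern holds. The start rules differ as written, the Program start depends partly on an early outcome, and nothing in the analysis section aligns them. Confidence in that is high.

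Size and sign are not known in advance. The reinitiation ranges are illustrations rather than bounds; they rest on the assumed 50% control refill by day 90, lag, Phase 1 share and Phase 2 uptake. They do not size the primary outcome, which also depends on when viral loads are drawn and whether results from before the window count. There the illustrative gap takes either sign, and confidence in its size is only moderate.

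Because the control group is not randomized, time zero is basic to the comparison. This should be corrected before the between-arm analysis is run.

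**What to change.** For the primary between-arm analysis, specify:

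1. a common time zero in both arms that does not depend on outcome;
2. the same no-ART-claim check at that date in both arms;
3. one fixed, pre-specified horizon, with no restart at Phase 2 or on joining PositiveLinks.

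One workable method is to match each Program participant to controls from the same monthly screen and days-late band who have no ART claim up to that participant's first-consultation date, and to use that date for both. Any equivalent alignment would do.

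Giving a control the participant's final-consultation end date is not equivalent, because that date still depends on the participant's early outcome. It leaves +0.5 to +5.4 points for reinitiation among Phase 1 entrants. The Table 1 clock can stay as a descriptive Program-arm analysis. The Outcomes sentence on control follow-up should be reworded to agree with the usual care Follow-up paragraph.

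**Cost.** Analysis-plan text and programming on data already held, plus one time-critical step: index dates must be assigned while records are still linked in the monthly integration, before control data are de-identified with no code key. The study must confirm that its agreements allow this. Fewer controls will qualify at each match date; the pool size is not stated, so the loss and the feasibility of close matching cannot be sized. Phase 2 recipients will have less time after their last consultation unless the common horizon is lengthened in both arms.

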Overview. Patient-level support in the program arm seeks to improve timely filling of ART prescriptions among participants with late ART prescription refill(s) by >30–365 days. The program arm will consist of up to two phases, which will be distinguished by the barriers primarily addressed in each phase. Both phases will involve phone consultations to discuss barriers to prescription adherence. Both phases also will provide referrals to resources that address participant barriers to timely filling of ART prescriptions. However, discussion with participants whose ART prescriptions fills have been late for a more extended period (>60 days) will focus on more complex barriers to filling ART prescriptions (e.g., substance use, unstable housing) and these participants will be additionally offered PositiveLinks, a warm health technology support to promote better health for people living with HIV. The phone consultations will be delivered by a linkage coordinator.

Patient-level support in the program arm will involve: 1) Screening, recruitment of eligible potential participants, 2) Informed consent, 3) Courtesy notification letter and study information sheet for providers, 4) Program implementation, and 5) Follow-up.

Screening, recruitment, and arm assignment. Screening and recruitment will occur as described previously.

Informed consent. Informed consent procedures will be conducted verbally by the linkage coordinator and follow identity verification. Informed consent will occur via phone at a time that is convenient for the eligible potential participant. Thus, informed consent may occur immediately following identity verification or at subsequently scheduled time. The complete informed consent process will precede program implementation. Subsequent telephone contact will involve reminders that participants may withdraw from the study at any time and for any reason without penalty; they will also involve opportunity for questions.

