We will use propensity score methods to control for potential confounding patient or provider characteristics that may affect the acceptance to enroll in the study and, consequently, the outcome of interest (HIV viral suppression, adherence, and reinitiation). Propensity score methods help us balance the distribution of the covariates between treatment and control groups, reducing the selection bias and allowing for more accurate causal inference when assessing the impact of the treatment. Propensity scores (PS) will be calculated as the predicted probabilities of being in the treatment group. Logistic regression model predicting being in the enrolled in the study will be used. A wide range of patient (age, gender, race, Medicaid enrollment, etc.), provider (specialty), hospital and geographical (region, rurality) characteristics will be considered in the regression model. We will use the PS to match the treatment group to the control group. We will calculate the inverse probability weights (IPW) using these PS. We will evaluate the effect of the program in the PS matched samples on the binary outcomes—including HIV RNA viral load <200 copies/mL (primary outcome), adherence (secondary outcome), and reinitiation (secondary outcome)—by comparing the proportions between the Program arm and the Usual Care arm. We will use Chi-squared tests to evaluate the statistical significance of the effects of treatments on proportions. We will also use logistic regression models to test for the program effects, adjusting for all potential confounders that might affect the outcome and bias the results.

Sample size and statistical power considerations

We expect to enroll 100 participants in the Program arm. This sample size provides adequate power to detect differences in HIV viral suppression (i.e., HIV viral load <200 copies/mL), the primary outcome, across arms. Assuming a 50% rate of viral suppression in the control group, with 100 subjects in the control group, we will be able to detect a difference of .28 in the rate of viral suppression with greater than 80% power. This requires a sample size of 350 participants in each arm. However, an estimated 30% of the sample will be missing HIV viral load data (Crepaz et al. *MMWR Morb Mortal Wkly Rep* 2018). This translates into dropping the power to 70%. According to our experience with these data, and the

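### Program-arm follow-up is defined only from a consultation, so a participant who consents but never has one is enrolled without an outcome window

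*Combined protocol and SAP*

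**What the plan says.** Under Procedures: Program arm, Follow-up, the rule is "A 3-month follow-up period will begin on the date of the final consultation". Table 1 applies it under the title "Start date of 3-month follow-up for participants receiving patient-level support". Its rows are Phase 1 only, Phase 2 only, and Phases 1 and 2. Each start date is a final consultation or, for those with both phases, the later of the final Phase 2 consultation and joining PositiveLinks.

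The Outcomes section gives the primary outcome no other anchor in this arm: "in the program arm, 3-month follow-up will be as shown in Table 1". The secondary outcomes have no separate start date.

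Consent is an earlier step. The Informed consent paragraph says "The complete informed consent process will precede program implementation", and that "participants may withdraw from the study at any time and for any reason without penalty". It allows consent to be given straight after identity verification or in a later scheduled call.

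The Statistical analysis section describes the Program group as the people enrolled in that arm, and its propensity score is meant to control for "characteristics that may affect the acceptance to enroll in the study". No intention-to-treat or other analysis set is defined.

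For controls, Procedures: Usual care arm starts the 3 months on the first date that the late refill is confirmed. Controls are not contacted and give no consent.

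**The concern.** The rule that fixes when the outcome is measured also decides, without saying so, who can have an outcome. In the Program arm a window exists only after the participant has engaged with a consultation. In the control arm it exists as soon as eligibility is confirmed. If the analyst applies Table 1 literally, the Program arm is conditioned on an event after enrollment and the control arm is not.

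Propensity matching as described does not address this. It models who enrolls, not who goes on to complete a call, and none of the covariates named as examples measures willingness to do so. People who consent and then cannot be reached, or withdraw before the consultation, may also be less engaged in HIV care. If so, leaving them out raises Program-arm suppression, adherence and reinitiation without any program effect. If the handling is settled only at analysis, it may be chosen with the outcomes in view.

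**Working it through.** **Step 1. Who has a window under the text as written**

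| Situation | Table 1 row | Start of 3 months |
|---|---|---|
| Phase 1 consultation, then fill, loss or refusal before Phase 2 | Phase 1 only | Final Phase 1 consultation |
| Enrolled directly into Phase 2, consultation held | Phase 2 only | Final Phase 2 consultation |
| Both phases | Phases 1 and 2 | Later of final Phase 2 consultation and joining PositiveLinks |
| Consented, no consultation | None | None |
| Control | Not applicable | Confirmed eligibility |

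Only the fourth line has no window. Someone who withdraws or is lost after a consultation still fits a row.

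**Step 2. Size of the bias if the fourth line is left out**

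Let P be the suppression rate among enrollees with a consultation, and P − d the rate among the fraction f without one.

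- Rate in everyone enrolled: (1 − f)P + f(P − d) = P − f × d
- Rate reported from recipients only: P
- Bias in favour of the program: f × d

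The documents give neither f nor d. With an assumed d of 20 points:

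- f = 5%: 0.05 × 20 = 1 point
- f = 10%: 0.10 × 20 = 2 points
- f = 20%: 0.20 × 20 = 4 points
- d = 0 (loss unrelated to outcome): 0 points at any f

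**Step 3. Cross-check under no true effect**

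Take 50% suppression in everyone enrolled (the plan's control rate) and let q be the rate in those without a consultation. The observed Program rate is (0.50 − f × q)/(1 − f). With f = 10% and q = 30% it is (0.50 − 0.03)/0.90 = 52.2%, a spurious gain of 2.2 points. Here d = 52.2 − 30 = 22.2, and f × d = 2.2, which agrees with Step 2.

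The next table gives the range over q = 40% down to 20%, with 100 × (1 − f) per arm. The test is taken as two-sided 0.05, because the plan states no alpha.

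| f | Spurious gain, points | Chance of a false finding for the program (nominal 2.5%) |
|---|---|---|
| 5% | 0.5 to 1.6 | 3.0% to 4.1% |
| 10% | 1.1 to 3.3 | 3.5% to 6.5% |
| 20% | 2.5 to 7.5 | 5.0% to 15.6% |

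At q = 50% the gain is zero.

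**Step 4. Scale against the plan's own figures**

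The plan gives no figure for this loss. Its nearest is a detectable difference of 0.28 from 50%, with more than 80% power at 100 controls and 100 Program participants. The pooled two-proportion formula gives 98.8%, so the inequality holds. With 95, 90 and 80 per arm, power is 98.4%, 97.9% and 96.5%. Loss of numbers is therefore not the issue; selective loss is. The standard error of the difference at 50% with 100 per arm is √(2 × 0.5 × 0.5/100) = 0.071, about 7 points.

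**The case against.** The strongest reply is that the plan never excludes these participants. It names the Program group as the people enrolled, and its propensity model predicts enrollment. That stands. A reader might infer that the Program arm becomes a completers group because the sample-size section says "no missing data are allowed". The documents do not support that. The sentence follows the estimate of missing viral loads and refers to experience with these data and to the inclusion and Medicaid–health department matching protocols. It concerns completeness of the linked data and is not a rule for deleting participants without a consultation. What remains is that Table 1 gives them no start date.

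The affected group may also be very small. Consent can follow identity verification at once, and consent and consultation may take place in one call. The plan gives neither the interval between them nor an expected loss. This stands too, and it is why the size can be given only as a range.

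Three further inferences should be resisted:

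- Controls are not unselected. They are propensity-matched, and they too can lack a viral load. The asymmetry is only that they cannot be lost through failed contact or withdrawal before follow-up starts.
- A reader might conclude that the consent process fails to separate stopping contact from stopping use of records. The protocol text is silent on this, but consent pages are not part of the text reviewed, so nothing can be concluded about them.
- The gap is not wholly separate from the difference in start dates. If Program follow-up began at confirmed eligibility, as for controls, every enrolled person would have a window, and only the analysis set would remain to be stated.

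Finally, a bias of 1 to 4 points is below one standard error and well below the planned 28 points. That limits the severity, but it does not remove the need for a rule on the primary outcome.

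**Conclusion.** The point holds as a defect in the definition of the primary outcome. An enrolled participant with no consultation has no outcome window, which conflicts with a comparison defined on enrollment, and the gap can arise in one arm only. It does not extend to people lost after a consultation, and the documents do not show that anyone is in fact to be excluded.

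If such participants are left out, the bias is f × d in favour of the program: 1 to 4 points for f of 5–20% and d of 20 points. Both inputs are assumptions. The direction rests on the further assumption that people who disengage before a consultation have lower suppression; without it, the bias is zero. This should be corrected because it concerns the primary outcome and costs little. With an unknown and possibly small number affected, it is not by itself a critical flaw.

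**What to change.** 1. State that the Program-arm analysis set, for the primary and secondary outcomes, is everyone enrolled (consented and confirmed eligible), whether or not a consultation was received. Because Other data and analyses describes a final eligibility check made through participant contact, say when that check falls relative to consent.
2. State that outcomes for this set are taken from the linked claims and surveillance records unless use of those records is revoked.
3. Use one start date for all Program participants that does not depend on receiving a consultation, preferably the one used for controls: confirmed eligibility, or a matched index date. Adding a consent-date row to Table 1 for non-recipients alone would not do, because it would put two clocks in one arm.
4. Report the result anchored on the consultation and limited to recipients as supplementary, with the number of enrolled participants who had no consultation.

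The cost is an analysis-set statement and a revised Table 1; the outcome sources are already part of the planned linkage. The downside is some dilution of the estimated effect, because people who received no support are counted and part of the window may precede the consultation. The change does not remove the separate contrast between volunteers and controls who were never approached.
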